5.3 Secondary Objectives

The secondary objectives of this study are to:

- Compare the difference in BOE (urinary total NNAL, nicotine metabolites, S-phenylmercaptmic acid [S-PMA], blood carboxyhemoglobin [COHb], and exhaled carbon monoxide [CO]) and CPD between two methods for determining CPD during the Baseline Period:
 - Recall of average daily CPD for prior week using Past 7 Day Cigarettes Use Questionnaire (Day I).
 - Daily CPD tracking using an IVRS (7 day average of values recorded on Days 2 through 8).
- Compare the differences in percent change in urinary nicotine equivalent (NE), S-PMA, blood COHb, exhaled CO, and CPD from Baseline to EOS between adult smokers randomly assigned to Test Group (*ad libitum* VBM-FG2 use) and Control Group (no VBM-FG2).
- Compare the changes in all BOE and CPD from Baseline to EOS between Test Group and Control Group over 4 weeks.
- Characterize subgroups based on change in CPD from Baseline to EOS (no change, <50% reduction, ≥50% reduction, 100% reduction, increase) within each study group.
- Characterize subgroups based on change in total NNAL from Baseline to EOS (no change, reduction, increase) within each study group.
- Compare changes in the Fagerstrom Test for Cigarette Dependence (FTCD) from Baseline (Day 8) to EOS within and between each study group.
- Compare changes on the Quit Attempts and Quitting Intentions from Baseline (Day I) to EOS within and between each study group.

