6. STUDY DESIGN

This is a randomized, controlled, open-label, parallel group, multi-center, 5-week pilot study to determine changes in BOE in adult smokers allowed *ad libitum* use of VBM-FG2 relative to adult smokers who are not allowed use of VBM-FG2. The data collected from this study will be used to estimate the variability of differences in the percent change from Baseline to the EOS in urinary total NNAL between Test and Control Groups; these findings will be used to estimate the sample size for a future pivotal study. This study will be conducted in approximately 150 adult

smokers who are considered to be in overall good health. Subjects will be randomized (based on gender, daily cigarette consumption [<20 and 20], and quit attempts [any quit attempts/no quit attempts]) to Test (allowed VBM-FG2 use) or Control (not allowed VBM-FG2 use) product in a 3:2 ratio (90 subjects randomized to Test: 60 subjects randomized to Control) with no more than a 60:40 distribution of either males or females to either group.

Screening	Baseline Period*		Product Use Period ^t			
Visit 1	Visit 2	Visit 3	Visit 4	Visit 5	Visit 6	Visit 7
Day -28 to Day -1	Day 1	Day 8±1	Day 15 ± 1	Day 22 ± 1	Day 29± 1	Day 36 ± 1
Subject evaluated against inclusion and exclusion criteria for study eligibility	Baseline CPD data gathered using recall of previous week and daily IVRS call.		Randomization in a 3:2 ratio (Test:Control) 
 • Test = ad libitum VBM-FG2 • Control = no VBM-FG2 			
Enrollment		Randomization				

*Baseline Period = after the daily IVRS call on Day 1 through the daily IVRS call on Day 8.

^t Product Use Period = after the daily IVRS call on Day 8 through the daily IVRS call on Day 36.

Note: Subjects in both groups are allowed to smoke their regular brand cigarettes during the entire study period

Expected duration of the study, from first subject first visit through last subject last visit is approximately 3 months. Expected duration for each subject is expected to be up to approximately 5 weeks (potentially 9 weeks from Screening to EOS). All subjects will be informed that they are allowed to smoke their own cigarettes or to quit smoking during the study.

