Covance will use the above formula to conduct some sample calculations and submit the results to ALCS for review. Appropriate modifications will be made if deemed necessary after the review.

Blood: COHb

Respiratory: Exhaled CO

Statistical Analysis Endpoints:

- Urine Creatinine Adjusted TotalNNAL
- Urine Creatinine Adjusted Nicotine Equivalents
- Urine Creatinine Adjusted S-PMA
- Unadjusted COHb
- Unadjusted Exhaled CO
- Total FTCD Score
- CPD
- VBM-FG2 use and other tobacco product use
- Quit Attempts and Quitting Intentions

The word "Adjusted" or "Unadjusted" will not be used while referring to the above statistical analyses endpoints later on but it will be adjusted/unadjusted based on the above list. The first 5 endpoints will be referred to as 5 BOEs.

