All secondary and exploratory analyses will be conducted on the Per-protocol population only.

A linear regression analysis will be conducted within each group at each timepoint to examine the relationships between levels of all 5 BOEs (dependent variable) with either weekly cigarette counts (Day 1 and 8 from questionnaire) or daily cigarette counts (from IVRS) (independent variable). For total NNAL, the corresponding daily cigarette counts from IVRS will be the average of past 7 days. For other biomarkers, it will be the average of past 2 days. The regression analysis will be conducted on the Per-protocol population.

The proportion of subjects in subgroups will be provided with proportion and sample size based on:

- 1) Cigarette consumption change from Baseline (average of Days 2 to 8 from IVRS) to the last week (no change, <50% reduction, 2::50% reduction , 100% reduction, increase);
- 2) Total NNAL change from Day 8 to the last visit (no change, reduction, increase);
- 3) Total scores of FTCD change from Day 8 to the last visit (increase, no change, decrease)
- 4) Proportion of subjects in subgroups based on Changes from Baseline (Day 1) to EOS (increase, no change, decrease) on the change in Quit Attempts from Day 1 to last visit.
- 5) Proportion of subjects in subgroups based on Changes from Baseline (Day 1) to EOS (yes to no, no to yes, and same) on the change in Quitting Intentions from Day 1 to last visit.

The Mantel-Haenszel Chi-Square Test will be used for (1), (2), (3), and (4); Fisher exact test will be used for (5) to test the frequency differences between the two groups.

Additional statistical analyses:

Wilcoxon signed rank test will be used to test the FTCD score difference between the 2 baseline measures (Visit 2 and 3) for the test group. If there is no statistical significance, the average score will be related to the average amount of VBM-FG2 in the past week via linear regression. Otherwise the FTCD score for Visit 3 will be used.

For the test group only, a simple linear regression model will be used to examine the relationship between COHb and Exhaled CO at each post-baseline visit.

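### The Mantel-Haenszel test for CPD change is specified without scores, on categories that overlap and are listed out of order; scored as listed, it can lose much of its power

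*SAP*

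**What the plan says.** SAP section 11.4.2 lists five classifications of subjects by change from baseline. For the first four it states "The Mantel-Haenszel Chi-Square Test will be used for (1), (2), (3), and (4", and the purpose is "to test the frequency differences between the two groups". Section 11.4 says that all analyses use SAS.

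- **CPD (item 1).** The categories are clearest in section 5.3: "no change, <50% reduction, ≥50% reduction, 100% reduction, increase". Sections 11.3.2 and 11.4.2 keep the same order, with increase last.
- **NNAL (item 2).** "Total NNAL change from Day 8 to the last visit (no change, reduction, increase". The order is the same in sections 5.3 and 11.3.2.
- **FTCD (item 3).** "Total scores of FTCD change from Day 8 to the last visit (increase, no change, decrease". This list runs in one direction, as does the list for quit attempts (item 4).

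The SAP gives no column scores, does not say that the listed order is the scoring order, and defines no band for no change. Section 11.4.2 restricts secondary analyses to the Per-protocol population.

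**The concern.** In a table of two groups by several columns, the Mantel-Haenszel chi-square tests linear association between group and column score. It works well when the scores follow the direction in which subjects are expected to move. The SAP names this test but leaves its deciding input open.

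The one order on offer for CPD is unsuitable. Scored as listed, an increase gets 5 and quitting gets 4. If Test moves subjects out of the increase column and into larger reductions, the two movements pull the mean score in opposite directions and partly cancel.

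Separately, the CPD cells are not disjoint. A reduction of 50% or more has no upper limit, so it contains 100%. Section 6 tells subjects that they may quit, so this cell can be occupied.

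FTCD and quit attempts, under the same test, are in graded order. A programmer therefore has no single convention to follow, and the p-value for CPD could rest on a coding choice that nobody wrote down.

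**Working it through.** The SAP states no power for these tests, so there is no figure of its own to reproduce. All category rates below are assumptions.

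**Inputs.** Group sizes are from section 6: "90 subjects randomized to Test: 60 subjects randomized to Control". A Per-protocol set of 72 and 48 (80% of each group) is assumed as a second case. The 5% level is stated in section 11.4.1 for product comparisons and is assumed here.

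**Statistic.** Q = (N − 1)r², where r is the correlation between group and column score, referred to chi-square with one degree of freedom.

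**One CPD scenario.** The categories are made disjoint.

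| Category | Test | Control | Listed score | Graded score |
|---|---|---|---|---|
| Increase | 0.20 | 0.40 | 5 | 1 |
| No change | 0.05 | 0.10 | 1 | 2 |
| >0 to <50% reduction | 0.50 | 0.42 | 2 | 3 |
| 50 to <100% reduction | 0.22 | 0.07 | 3 | 4 |
| 100% reduction | 0.03 | 0.01 | 4 | 5 |

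1. Listed scores. Mean, Test: 0.05×1 + 0.50×2 + 0.22×3 + 0.03×4 + 0.20×5 = 2.83. Control: 0.10×1 + 0.42×2 + 0.07×3 + 0.01×4 + 0.40×5 = 3.19. Difference −0.36.
2. Graded scores. Mean, Test: 0.20×1 + 0.05×2 + 0.50×3 + 0.22×4 + 0.03×5 = 2.83. Control: 0.40×1 + 0.10×2 + 0.42×3 + 0.07×4 + 0.01×5 = 2.19. Difference +0.64.
3. Variances (mean of squared scores minus squared mean). Listed: 9.51 − 2.83² = 1.50 (Test) and 12.57 − 3.19² = 2.39 (Control). Graded: 9.17 − 2.83² = 1.16 and 5.95 − 2.19² = 1.15.
4. Normal approximation at 90 and 60. Listed: SE = √(1.50/90 + 2.39/60) = 0.238, |z| = 0.36/0.238 = 1.51, power ≈ Φ(1.51 − 1.96) = 0.33. Graded: SE = √(1.16/90 + 1.15/60) = 0.179, z = 0.64/0.179 = 3.57, power ≈ Φ(3.57 − 1.96) = 0.95.
5. Simulation of Q in the same scenario: 0.35 listed against 0.94 graded at 90 and 60; 0.30 against 0.88 at 72 and 48.
6. A similar scenario with the no-change cell empty: 0.62 listed against 0.93 graded.

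**Is the loss due to the scores?** In a second scenario, listed order, Test is 5/45/30/5/15% and Control 10/45/10/0/35%. Power is 0.22 with listed scores, 0.99 with graded scores and 0.95 with Pearson's chi-square, which ignores order. The information is in the table; the scores discard it.

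**Range for CPD.** Thirty scenarios at 90 and 60 used a normal percent change with SD 25 or 35, five pairs of group means, quit rates of 0 to 5%, and a no-change band of 0, ±2.5 or ±5 points. Power was 0.08 to 0.71 with listed scores and 0.56 to above 0.99 with graded scores. Power retained ran from 84% (0.67 of 0.80) down to 8% (0.08 of 0.99). More than half was lost in 19 of 30 scenarios, but in only 4 of the 10 with an empty no-change cell.

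**NNAL.** The analysis variable is "Urine Creatinine Adjusted TotalNNAL", a continuous value. With no band, almost nobody is exactly unchanged and two columns are occupied. Any two distinct scores are then linear transforms of each other, so r² does not depend on them. With SD 40 and a group difference of 20 to 25 points at 90 and 60:

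| No-change band | Listed | Graded |
|---|---|---|
| None | 0.65–0.83 | 0.65–0.83 |
| ±1 point | 0.57–0.75 | 0.66–0.83 |
| ±5 points | 0.38–0.51 | 0.69–0.86 |
| ±10 points | 0.24–0.31 | 0.72–0.88 |

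More than half is lost only from about ±10 points, a band that the SAP does not contain.

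**The case against.** The strongest reply is that the lists in section 11.4.2 introduce subgroups for tabulation and assign no scores. A graded coding is as compatible with the text as the listed one, and table detail is left to a shell document that is not at hand. This stands: a reader might infer that the SAP mis-scores the CPD categories, and it does not say so. What remains is that a score-dependent test has no scores and the only written order is a poor one.

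A reader might also infer that the test loses most of its power. That is too strong. The loss depends on listed-order scoring and on assumed rates, and it is moderate in many scenarios with an empty no-change cell. CPD change compares averages over a week, so exact equality may be uncommon. Nor does the overlap cost power: reading the fourth-ranked category as 50 to <100% removes it. The overlap is a classification fault.

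It is tempting to conclude that a real shift in smoking would be missed. Section 11.4.2 also analyses CPD change as a continuous outcome in mixed models, section 11.4.1 does so for NNAL, and the subgroup proportions are reported whatever the test shows. Nor is a reversed trend at issue: the statistic is squared and no trend estimate is planned.

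Finally, this is a pilot with no power claim for any endpoint. That limits the weight of the point, but a between-group test named for a secondary endpoint should still be reproducible from the text.

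**Conclusion.** The point holds for CPD as a defect of specification. The overlap, the ungraded order and the absence of scores can be read directly from the SAP and need no assumed rate.

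The power figures are conditional. They assume the one-degree-of-freedom statistic, scores that follow the listed order, the 5% level and invented category rates. On those terms power falls from 0.94 to 0.35 in one scenario and from 0.93 to 0.62 with an empty no-change cell, within a range from slight to nearly total loss. The documents give no rates that would narrow it.

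For NNAL the order is worth tidying, but little or no power is at stake unless a no-change band is introduced. The primary analysis and the mixed models for CPD are not affected.

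**What to change.** In section 11.4.2, and to match in sections 5.3 and 11.3.2, define the CPD categories as disjoint and ordered: increase; no change; >0 to <50% reduction; 50 to <100% reduction; 100% reduction. State that the Mantel-Haenszel test uses scores 1 to 5 in that order. Order NNAL as increase, no change, reduction. Say whether no change means exact equality or a band, since the NNAL order starts to matter once that cell is filled.

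The cost is a few lines of SAP wording and the format order in the program. No data collection or sample size changes. It should be settled before the database lock, so that the coding is not chosen with the results in view.

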11. STATISTICAL METHODOLOGY

11.1 General

Data listings will be provided for all subjects up to the point of withdrawal, with any subjects excluded from the relevant population highlighted. Summary statistics and statistical analyses will generally only be performed for subjects included in the relevant analysis population. For the calculation of summary statistics and statistical analysis, unrounded data will be used. For continuous data, summary statistics will include the number of non-missing values (N), mean, median, standard deviation (SD), minimum (min), maximum (max). For categorical data, frequency counts and percentages will be presented.

Mean change from baseline is the mean of all individual subjects' change from baseline values. Each individual change from baseline will be calculated by subtracting the individual subject's baseline value from the value at the timepoint. The individual subject's change from baseline values will be used to calculate the mean change from baseline using a SAS® procedure such as Proc Univariate.

Mean percent change from baseline is the mean of all individual subjects' percent change from baseline values. Each percent change from baseline will be calculated by subtracting the individual subject's baseline value from the value at the desired timepoint and then dividing this calculated value by the individual subject's baseline value and multiplying by 100. These

individual subjects' percent changes from baseline values will be used to calculate the mean percent change from baseline using a SAS® procedure such as Proc Univariate.

Missing values will not be imputed.

Data analysis will be performed using SAS® Version 9.1.3 or higher.

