A stepwise multiple linear regression model will also be used to examine the relationship between each of the 5 BOEs (response variable) and a number of factors including average CPD, average VBM-FG2 use, average use of other products, age, sex, BMI and race at each post-baseline visit for the test group only. The average amount of tobacco product use will be for the past 7 days when total NNAL is the dependent variable and will be for the past two days when other BOE is the dependent variable.

Demographics and Characterization of Tobacco Product Use and Exposure Patterns

Demographic baseline characteristics will be summarized by study group with descriptive statistics. For continuous data, descriptive statistics will include N, mean, median, SD, min, max, coefficient of variation (CV%), and 95% confidence interval (CI). For categorical data, frequency counts and percentages will be presented. Fisher's exact test will be used to test for the differences in categorical variables (sex, race: White versus Non-white, quit attempt, cigarette consumption per day: ≤ 20 and > 20) between the 2 study groups and t test, to test for the differences in continuous variables (age, body weight, height, BMI, Number of times stopped smoking cigarettes for 24 hours or longer in an attempt to quit in past 6 months, Number of years smoked since turning 21 years).

Descriptive statistics will be provided to summarize the use of all tobacco products including cigarettes, VBM-FG2 discs and other products by study group and visit. The mean for each variable will be plotted by study group over time.

For subjects in the test group, a simple linear regression model will be used to examine the relationship between visit average of CPD (from IVRS) and visit average of VBM-FG2 use for all post-baseline visits in the study.

For subjects in the test group, a frequency table will be provided with the responses (definitely would buy and probably would buy) in the VBM-FG2 Potential Purchase Interest Questionnaire as the row variable and their average VBM-FG2 use level (4 discs versus < 4) in the last 2 visits as the column variable. Fisher exact test will be used to test for the association.

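### Stepwise selection decides whether VBM-FG2 use stays in the only SAP analysis relating it to biomarker levels; if its true effect is small, the slope is often dropped, and inflated when kept (minor)

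*SAP*

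**What the plan says.** SAP section 11.4.2, among the additional analyses: "A stepwise multiple linear regression model will also be used to examine the relationship between each of the 5 BOEs (response variable) and a number"; the candidate terms it names are "average CPD, average VBM-FG2 use, average use of other products, age, sex, BMI and race at each post-baseline visit for the test group only". Section 11.2 gives Visits 4 to 7 as the post-baseline visits for the biomarkers.

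The SAP gives no entry or stay threshold, forces no variable into the model, and does not say whether the disc-use slope is shown when the term is not selected.

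Three other statements fix the amount of data:

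- Section 6: "90 subjects randomized to Test: 60 subjects randomized to Control".
- Section 11.4.2: "All secondary and exploratory analyses will be conducted on the Per-protocol population only".
- Section 11.1: "Missing values will not be imputed".

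**The concern.** The stated aim is to examine a relationship. That calls for an estimate with its uncertainty at each visit, including when the estimate is close to zero. Stepwise selection answers a different question, namely which terms pass a threshold in this sample. Three things follow.

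- **Omission.** A weak disc-use term tends to be left out, and no other analysis in the SAP text supplies its slope.
- **Inflation.** A weak term gets in only when chance has made its estimate large. The usual slope, interval and P-value take no account of that.
- **Comparability.** The other terms kept can differ between visits and biomarkers, so two reported disc-use slopes may be adjusted for different things.

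At stake is the description of how biomarker levels vary with the amount of VBM-FG2 used.

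**Working it through.** **1. Is this the only such analysis?** The SAP analyses that involve a biomarker or the amount of disc use are:

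| Analysis | Outcome | Predictor of interest |
|---|---|---|
| Mixed models (11.4.1, 11.4.2) | Change in biomarker | Study group; Model 2 adds CPD and demographics |
| Regression at each timepoint (11.4.2) | Biomarker level | Cigarette counts |
| COHb and exhaled CO regression (11.4.2) | One CO marker | The other CO marker |
| FTCD regression (11.4.2) | FTCD score | Disc use |
| CPD regression (11.4.2) | CPD related to disc use | Disc use |
| Purchase-interest table (11.4.2) | Purchase interest crossed with disc use | Disc use |
| Stepwise regression (11.4.2) | Biomarker level | Disc use among 7 named factors |

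Only the last has a biomarker as outcome and amount of disc use as predictor.

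**2. Number of selections and sample size.** 5 biomarkers × 4 visits = 20 selections. The Test group is 150 × 3/5 = 90 at randomization. The Per-protocol restriction and the absence of imputation can only lower that. No dropout rate is given, so n = 70 and n = 90 were taken as a range.

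**3. Hand check of the inflation.** The SAP gives no figure to reproduce. Assume residual SD 1, standardized disc use, a disc-CPD correlation of -0.3 and all seven terms fitted. The approximate standard error of the disc-use slope is 1/√[(n − 8)(1 − 0.3²)].

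- n = 90: 1/√(82 × 0.91) = 0.116. To be significant the slope must exceed 1.989 × 0.116 = 0.23 at threshold 0.05, or 1.453 × 0.116 = 0.17 at 0.15.
- n = 70: 1/√(62 × 0.91) = 0.133. The corresponding bars are 1.999 × 0.133 = 0.27 and 1.458 × 0.133 = 0.19.

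A true slope of 0.1 therefore passes only if its estimate is roughly 1.7 to 2.7 times too large. A true slope of 0.5 passes easily without any help from chance.

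**4. Simulation.** Forward entry with backward removal, 7 candidates, equal entry and stay thresholds of 0.05 or 0.15, n = 70 or 90, CPD slope 0.5 residual SD per SD, disc-CPD correlation -0.3, 2,000 data sets per setting. All of these values are assumptions except the list of candidates and the ceiling of 90. Ranges run over n and threshold.

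| True disc-use slope | Dropped | Mean slope when kept ÷ truth | 95% CI coverage when kept |
|---|---|---|---|
| 0.1 | 71-87% | 2.2-3.0 | 77-86% |
| 0.2 | 37-66% | 1.3-1.7 | 92-95% |
| 0.3 | 13-41% | 1.1-1.25 | 96-97% |
| 0.5 | 0-5% | about 1.0 | 94-96% |

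With no true effect, disc use was still selected in about 5% (threshold 0.05) or 16% (threshold 0.15) of runs. Coverage when selected was then 0% or 57-63% respectively.

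Varying the correlation at n = 90 and threshold 0.15 (1,000 data sets each) changed little. At a true slope of 0.1 the term was kept in 31% of runs (correlation 0) or 26% (correlation -0.6), with inflation of 2.2 and 2.4 times.

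**5. Comparator.** The full seven-term model on the same simulated data gave mean slopes of 0.10, 0.20, 0.30 and 0.49-0.50 for true values of 0.1, 0.2, 0.3 and 0.5, with coverage of about 94-96%. It reports the slope every time.

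**The case against.** The strongest reply is that this is an additional analysis in a pilot. A disc-use slope appears in no objective (sections 5.2 and 5.3) and no primary or secondary endpoint (sections 11.3.1 and 11.3.2). Section 4 says some added analyses are exploratory, and screening a list of factors is an ordinary exploratory use of stepwise regression. The SAP promises no slope that is comparable across visits. This stands, and it sets the priority. It does not remove the point, because an exploratory slope is still read as an estimate.

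A second reply is that the size depends on assumptions. This also stands: the SAP gives neither a threshold nor an expected effect for any biomarker, and one set of effects need not suit all five. The discs deliver nicotine, so nicotine equivalents may respond differently from the other markers. With a strong effect the problem nearly vanishes.

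Third, the table shells are not shown and may display unselected terms, and the list of factors is introduced as inclusive rather than closed. Both are fair cautions. Neither affects the inflation of slopes after selection.

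A reader might go further and infer that biased slopes would mislead planning of the pivotal study. The SAP does not support that. Sections 6 and 8 say that what feeds the pivotal sample size is the variability of the primary outcome. The interim analysis in section 12, whose purpose is pivotal planning, is specified as descriptive statistics and frequencies, and its table list in Appendix 2 contains no regression output.

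A reader might also take omission and inflation as certain. They are large only if the true slope is small.

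**Conclusion.** The point holds, at minor priority. Stepwise selection suits the stated aim poorly, and the SAP text contains no other analysis to fall back on when disc use is dropped. For a small true slope (0.1 SD per SD) the planned analysis would usually omit the term and would overstate it two- to threefold otherwise. At 0.3 the overstatement is modest, and at 0.5 it is practically nil. These sizes rest on the assumed n, thresholds, CPD effect and disc-CPD correlation. That the adjustment set can vary between visits and biomarkers does not depend on them. The primary NNAL comparison and the variance estimate for the pivotal study are untouched.

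**What to change.** In section 11.4.2, replace the stepwise selection with one pre-specified linear model per biomarker and post-baseline visit in the Test group, containing all the listed terms: "average CPD, average VBM-FG2 use, average use of other products, age, sex, BMI and race". Keep the averaging windows the SAP already sets (7 days for total NNAL, 2 days for the others). Report the CPD and VBM-FG2 slopes with 95% CIs at every visit, whatever their P-values.

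The cost is about one sentence of SAP text and simpler programming. The downside is slightly wider nominal intervals than a reduced model would show. With 70 to 90 subjects, seven terms gave close to nominal coverage in the simulation, so sample size gives no reason to select.

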7. STUDY PRODUCT

The VBM-FG2 discs are oral, non-dissolvable products containing tobacco-derived nicotine (approximately 1.5 mg/disc) that may provide an opportunity for adult cigarette smokers to move down the continuum of risk. These discs are a tobacco-derived nicotine product designed to appeal to adult cigarette smokers who are interested in tobacco product alternatives to cigarettes. These discs are designed to be spit-free and chewable.

Subjects in the Test Group will be provided VBM-FG2 discs and told to use them *ad libitum* throughout the study.

The groups will be presented in the TFLs as follows:

Study Group	Abbreviation
Subjects allowed ad libitum use of VBM-FG2	Test
Subjects not allowed use of VBM-FG2	Control

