11.2 Definition of Baseline for Calculating Change

The Baseline Period is from Day 1 to Day 8. The baseline for calculating change from baseline will be defined in the following table.

Metric	Baseline	Corresponding post-baseline visits
Quit Attempts and Quitting Intentions	Day 1 (Visit 2)	Day 36 (Visit 7)
Fagerstrom Test for Cigarette Dependence (FTCD)	Day 8 (Visit 3)	Day 36 (Visit 7)
BOE	Day 8 (Visit 3)	Visits 4, 5, 6, 7
CPD daily tracking from IVRS	The average of available data from Day 2 through Day 8	Daily CPD Day 9 to 36 or the average of last week at Visits 4, 5, 6, 7
Vital Signs	Day 8, including unscheduled (rechecked) values	Visits 4, 5, 6, 7
*see Section 11.4.3 for more details		

Rationale for the baseline choices for calculating change:

Quit attempts and intentions: Day 1 is the only one measurement in baseline.

FTCD: There are 2 measurements in the baseline, Day 1 and 8. Day 8 is selected because it is anticipated that there will be changes in CPD, a key component of the FTCD score, when adult smokers are asked to track their daily cigarette consumption. Day 1 value does not reflect this change.

BOE: Day 8 is the last of the 2 baseline values and is closer to the post-baseline values.

CPD daily tracking: The weekly average was selected to adjust for the daily variability and also because total NNAL (primary end-point) has a longer half-life and the average CPD might be better representative of changes in exposure to total NNAL than the individual values.

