11.4.2 Statistical Analyses of Secondary Endpoints

Difference in baseline:

Paired T Test will be used to examine the difference in all 5 BOEs between Day 1 and Day 8.

Paired T test will also be used to examine the differences in CPD between the once weekly recall at Day 8 (from questionnaire) and the average daily tracking of CPD from Days 2 through 8 (from IVRS).

Difference in change from baseline:

Linear mixed model for repeated measures analyses of variance will be used for the analyses of the secondary outcome measures: percent change from baseline and absolute change from baseline in all other BOEs. The same model will be used for percent change from baseline and absolute change from baseline in CPD and Total score of FTCD, the model details are as follows:

For other BOEs:

Model 1:

Percent (or absolute) change from baseline = study group + visit+ study group*visit + subject + random error

Model 2:

Percent (or absolute) change from baseline = study group+ visit+ study group*visit + subject + CPD + sex + race + BMI + age + random error

For CPD and Total Score ofFTCD:

Model 1:

Percent (or absolute) change from baseline = study group+ visit+ study group*visit +subject+ random error

Model 2:

Percent (or absolute) change from baseline = study group+ visit+ study group*visit +subject+ sex + race + BMI + age + random error

where

CPD = fixed effect covariate representing average number of cigarettes per day for the past two days from IVRS

study group = fixed effect term (test or control)

sex = fixed effect (male or female)

age = fixed effect covariate (continuous)

race= fixed effect (White or Non-White)

BMI = fixed effect covariate (continuous)

visit= fixed effect term representing days (ordinal categorical variable)

subject = random effect

baseline = Day 8 value for BOE and average of Day 2 to 8 for CPD (IVRS)

If the study group*visit interaction term is not statistically significant (P-value > 0.10), then the interaction term will be removed from the model and all comparisons will be done using the overall product means. If the interaction effect is significant (P-value < 0.10), then the comparisons will be conducted for each study visit.

Least squared mean and standard error for the product effect will be estimated by study group and visit with p-values for statistical significance. P-value will also be provided for other effects in the model.

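### The Test-group regression relating cigarettes per day to disc use omits baseline CPD, so its slope is imprecise and may be shifted by prior smoking intensity (minor)

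*SAP*

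**What the plan says.** The regression stands in SAP section 11.4.2, under the heading on demographics and characterization of tobacco product use. Its stated task, within the Test group and over Visits 4 to 7, is to "examine the relationship between visit average of CPD (from IVRS) and visit average of VBM-FG2 use". The SAP calls the model a simple linear regression, which has one predictor, so there is no place in it for baseline CPD. Both variables are post-baseline levels. The text does not say which is the response, and does not give a purpose beyond examining the relationship.

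Section 11.2 defines a baseline for IVRS-tracked CPD: "The average of available data from Day 2 through Day 8". Other parts of section 11.4.2 use it. For the mixed models, "The same model will be used for percent change from baseline and absolute change from baseline in CPD and Total score of FTCD", with study group, visit and their interaction as the main terms. The categories of CPD reduction are also counted from that baseline and compared between groups.

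The amount of disc use is not assigned. Section 7 states that Test subjects are "told to use them *ad libitum* throughout the study". Section 6 plans "90 subjects randomized to Test: 60 subjects randomized to Control". Section 11.4.2 restricts secondary and exploratory analyses to the Per-protocol population.

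**The concern.** Randomisation protects the comparison of Test with Control. It does not protect a comparison, within Test, of subjects who chose many discs with subjects who chose few. Smoking intensity before the product was given differs between subjects, and the SAP recognises this by making it a randomisation factor ("Subjects will be randomized (based on gender, daily cigarette consumption", section 6). If heavier smokers take more discs, or fewer, that pattern enters the slope together with any change in smoking that goes with disc use.

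There is a second cost that needs no such correlation. A level of CPD carries the whole between-subject spread of baseline CPD into the residual, although that spread is measured and could be removed.

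In the SAP text this is the only planned analysis that relates CPD to the amount of discs used. The mixed models relate change in CPD to study group, and the stepwise models have a biomarker as response. A reader who wants to know how smoking varies with the amount of disc use has only this slope. Both points apply at a single visit and do not depend on how repeated visits are handled.

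**Working it through.** The SAP states no figure for this regression, so there is none to reproduce. The check uses the omitted-variable formula and a standard-error calculation.

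**From the SAP:** one predictor; post-baseline levels; 90 subjects planned in Test; baseline CPD available from IVRS Days 2 to 8.

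**Assumed, not in the SAP:** SD of baseline CPD 7 (range 5 to 10); SD of discs per day 3 (range 2 to 5); residual SD 3; true reduction s of 0.5 or 1.0 cigarettes per extra disc; correlation rho between baseline CPD and disc use from −0.2 to 0.5. For the standard errors: 80 subjects at one visit, and baseline CPD measured with error SD 1.5.

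**Step 1, shift of the slope.** Let post-baseline CPD = baseline CPD − s × discs + error. The simple slope of CPD on discs is then

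slope = −s + rho × SD(baseline CPD) / SD(discs).

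With s = 0.5, 7/3 = 2.33:

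| rho | −0.2 | 0 | 0.1 | 0.2 | 0.3 | 0.4 |
|---|---|---|---|---|---|---|
| simple slope | −0.97 | −0.50 | −0.27 | −0.03 | +0.20 | +0.43 |
| simulated trials with slope above 0 (n = 90) | 0% | 4% | 17% | 46% | 78% | 96% |

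The slope is zero at rho = s × SD(discs) / SD(baseline CPD) = 0.5 × 3/7 = 0.21. With s = 1.0 it is zero at 3/7 = 0.43. Over the assumed SD ranges the turning point runs from 0.5 × 2/10 = 0.10 to 0.5 × 5/5 = 0.50 for s = 0.5, and from 0.20 to 1.0 for s = 1.0.

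**Step 2, with baseline CPD in the model.** In the same simulation (1000 runs per setting, baseline measured without error) the adjusted slope averaged −0.5 for s = 0.5 and −1.0 for s = 1.0 at every rho tried. With baseline error SD 1.5, a little bias remains: at rho = 0.3 and s = 0.5 the adjusted slope averages −0.47.

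**Step 3, precision at rho = 0, n = 80.**

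- Without baseline: SE ≈ √(49 + 9) / (3 × √80) = 7.62 / 26.83 = 0.28.
- With baseline measured with error SD 1.5: the baseline variance left unexplained is 49 × 2.25 / (49 + 2.25) = 2.15, so SE ≈ √(9 + 2.15) / 26.83 = 3.34 / 26.83 = 0.12.
- Chance of detecting a slope of −0.5 at the two-sided 5% level (normal approximation): 0.5/0.284 = 1.76, about 42%; 0.5/0.1245 = 4.02, about 98%.

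**The case against.** The strongest reply is that the SAP asks only for a relationship, in a section of descriptive summaries. If the question is whether those who smoke more also use more discs, the level-on-level slope is the right quantity and baseline intensity is part of the answer. That stands, and it is a reason to keep the simple slope. It does not answer the loss of precision for anyone who wants to see how CPD varies with disc use among subjects of similar prior smoking.

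A reader might infer that the plan has no sound test of whether discs lower smoking. The document does not support this. The randomised comparison of change in CPD and the between-group comparison of reduction categories both address the effect of access to discs, and both use the Days 2 to 8 baseline. What is unadjusted is a within-arm association with the amount used.

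A reader might also infer that the slope will hide or reverse a replacement effect. The document gives no value for rho, for either SD or for the effect per disc. At rho = 0 there is no bias, and a negative rho exaggerates the reduction. Reversal is a possibility under some assumed values and nothing more.

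The plan also relates baseline FTCD score to disc use, and one FTCD item is cigarettes per day. That gives a partial look at whether prior smoking goes with disc use, but does not adjust this slope.

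Finally, adjustment for baseline does not make the slope causal. In the simulation baseline CPD is the only confounder; in the trial, motivation to quit, dependence and other tobacco use may drive both discs and cigarettes. This stands and limits what the adjusted slope can be called.

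**Conclusion.** The point holds in a limited form. The simple regression leaves out a baseline that the SAP has already defined. Its slope can mislead if read as the number of cigarettes replaced per disc, with a direction and size that cannot be known from the document. The loss of precision does not need any correlation: under the assumed SDs the standard error is more than twice what it need be (0.28 against 0.12). The ratio depends on those SDs and shrinks if baseline CPD varies less between subjects or tracks later CPD less closely.

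Severity is minor. This is a supportive Per-protocol analysis in one arm of a pilot study. It does not affect the primary NNAL comparison or the variability estimate for the pivotal study.

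**What to change.** In SAP section 11.4.2:

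1. Keep the planned simple slope and label it as a description of concurrent use.
2. Add a Test-group model with post-baseline CPD as the response, disc use as the predictor of interest and the IVRS Days 2 to 8 average CPD as a covariate. This is preferable to change in CPD as the response, because a change score forces the baseline coefficient to be 1 and stays biased if heavier smokers cut more in absolute terms and rho is not zero.
3. Report the adjusted disc-use slope with its 95% CI, and state that it is an association and not a causal replacement rate.

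The cost is one covariate and a few lines of text; the data are already collected. Subjects with no IVRS baseline drop out of the adjusted model, since missing values are not imputed (section 11.1), so the number analysed should be shown for both slopes.
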